Drs. [name], [name] and [name] will work closely with the statistician ([name]) to design forms and a database that maximize accurate data entry. Common data elements will use the standardized codes and attempts will be made to harmonize all database codes with NIH initiatives. To minimize data-entry error and data-management miscoding, questionnaire data will be collected via tablet computers and immediately uploaded to a secure web-based server, ensuring backup. The electronic files from all sites will be merged into one REDCap data management file. Summary results will be entered into the larger REDCap database. Source documents and electronic data will be checked for accuracy and adherence to study protocols.

Data Storage:

Consent forms and subject lists will be stored in locked file cabinets separate from subject data and on password-protected computers, and will be only accessible to the research team. All subject data will be labeled only with a code number. These coded data will be kept separate from the master list that links subjects and their code numbers. All subject data will be kept in locked file cabinets in a locked office. Coded data stored on the computer will be maintained in password-restricted files. Any breach in confidentiality will be reported to the PIs.

Statistical Considerations

The primary outcome will be systolic BP at 12 months and secondary outcome will be non-HDL cholesterol at 12 months, both measured at 4 time-points (0, 4, 8, and 12 months). All BPs used for outcomes will be obtained by a blinded research assistant and cholesterol levels will be measured by lab personnel who are also blinded to treatment group. Because the outcomes are continuous, linear mixed-effects models⁸⁹ (LMM) will be used to examine the differences over time between the study arms. LMM will allow us to implicitly account for the correlation between a patient's repeated measurements over time. The general mean structure of the LMM we will use to examine the hypotheses is, $Y_{ij} = \beta_0 + \beta_1 * I(month = 4) + \beta_2 * I(month = 8) + \beta_3 * I(month = 12) + \beta_5 * arm * I(month = 4) + \beta_6 * arm * I(month = 8) + \beta_7 * arm * I(month12)$, where Y_{ij} represents the outcome of interest (i.e., SBP or non-HDL) for patient i at time j . In this model, we fit a common intercept and arm is the intervention group indicator. Similarly, time is classified, where for example, $I(month = 12)$ is a dummy variable equal to 1 for the 12 month time point. Random intercepts will be included for

each individual to account for correlation among repeated measurements over time. The primary analytic model will adjust for clinic site. The mixed effects model parameters will be estimated and tested using SAS PROC MIXED (SAS Institute, Cary, NC), and the hypothesis of between-arm differences over time will be tested using estimate statements within PROC MIXED. In particular, β_7 , the estimated difference in outcome between arms at 12 months, will be the primary effectiveness outcome assessed.

For the tertiary outcome of cascade category, we will calculate an ordinal four-level variable at baseline, 4, 8, and 12 months. We will use a proportional odds model fit via generalized estimating equations to examine differences over time between study arms. The proportional odds assumption will be assessed using score tests, and the model will be relaxed to partial proportional odds if necessary. Robust sandwich standard errors will be used to account for potential overdispersion and correlation among the repeated observations over time. Similarly to the primary analysis, the model will adjust for clinic site and include the same general mean model specification. The primary hypothesis will be tested via SAS PROC GENMOD to assess whether the estimated proportions in each level at 12 months differ between arms. All analyses will be conducted following an intention to treat (ITT) principle.

Missing Data:

We will assess mechanisms for missing data in this study. LMM, implicitly accommodates missingness when the response is Missing At Random (MAR); that is, when missingness is due either to treatment, to prior outcome, or to other baseline covariates included in the LMM. We will address missing data by imputing missing values using multiple imputation procedures as described by Schafer. Once missing values have been imputed, each multiply-imputed data set can be analyzed using the LMM. Final parameter estimates and their standard errors will be calculated using Rubin's formula. We will analyze our data and report final study results with and without employing the multiple imputation strategy (compared to complete case analysis) and carefully examine and describe any discrepancies found.

Power:

The power calculation for this study was based on our prior nurse-led BP intervention¹², a meta-analysis of cholesterol medication adherence interventions⁴², and baseline blood pressure and cholesterol data from our clinic sites. Power estimates were derived empirically via simulation in SAS 9.4. Simulated data were generated based on estimates from prior studies, such that we assumed a mean SBP at baseline of 145mmHg for both arms, with a reduction in the education control arm of 1mmHg by 12 months. For the intervention arm, we evaluated effect sizes (differences from education control at 12 months) of 5-7mmHg. We estimate that 15% of patients may drop out by the 12-month time point, and incorporated missing values into the simulated data based on a uniform pattern of 5% missing at 4 months, 10% at 8 months, and 15% at 12 months. The drop-out rate is consistent with prior interventional studies at our sites (80-88% retention at 12 months).^{11,12,90} We conservatively estimated variance components assuming a total standard deviation of 17 and a within-individual correlation of 0.4 among repeated SBP measurements. Similarly, for the secondary non-HDL outcome, we assumed a baseline value of 132mg/dL with a standard deviation of 41 and a within-individual correlation of 0.7, and evaluated sample size needed over effect sizes ranging from 10-20mg/dL.

After generating 1,000 simulated datasets under these assumptions, we fit the LMMs described above to each and assessed the effect of interest using two-sided tests with a type I

error rate of 0.05. Based on results, we will have >80% power to detect a 6mmHg lower systolic BP and >90% power to detect a 15mg/dL lower non-HDL cholesterol in the intervention arm vs. education control. Table 5 displays the sample sizes needed to detect a range of plausible *clinically significant* BP and non-HDL effects. A 6 mmHg improvement in systolic BP is associated with a ~20% decrease in ASCVD events⁹¹, and a 15mg/dL improvement in cholesterol is associated with ~10% decrease in clinical ASCVD events³¹.

Table 5: Sample size estimates to detect a range of plausible and clinically significant effect sizes						
	BP Effect Size			Non-HDL Effect Size		
	5mmHg	6mmHg	7mmHg	10mg/dL	15mg/dL	20mg/dL
70% Power	278	190	140	248	110	64
80% Power	350	234	178	310	148	80
90% Power	466	340	232	424	184	104

Green cells represent sample sizes that are less than our proposed sample size (n=300).

Pre-specified sub-group analyses of the primary, secondary, and tertiary outcomes will include clinic site, sex, and baseline ASCVD risk (<20% 10-year risk⁹² vs. >20% or prior ASCVD). For each category, we will examine the interactions with intervention arm and time. Generally, the modeling approach will mirror that described above for each outcome. Three separate analyses for each outcome will be conducted to assess the effect of each potential moderator. Models will be fit in SAS PROC MIXED and GENMOD, as described above, and the moderating effect of each of the three factors will be assessed via the hypothesis test of the three-way interaction among subgroup, treatment, and time at 12 months.

ClinicalTrials.gov requirements

This application includes a trial that requires registration in ClinicalTrials.gov. The registration number for this trial is NCT03643705.

Multiple Principal Investigator Leadership Plan

This project will have three NIH co-Principal Investigators (co-PI) and a fourth University Hospitals Principal Investigator to oversee the IRB:

1. **[name], MD (NIH contact PI)**—Associate Professor of Medicine; University of Washington School of Medicine; Seattle, WA
2. **[name], PhD (NIH MPI)**—Research Professor of Population Health, Medicine, Psychiatry, and Nursing; Department of Population Health Sciences; Duke University School of Medicine; Durham, NC
3. **[name], RN PhD (NIH MPI)**— Professor of Nursing; University of Washington School of Nursing; Seattle, WA
4. **[name], MD (UH IRB PI)**—Professor of Medicine; University Hospitals Cleveland Medical Center and Case Western Reserve University School of Medicine; Cleveland, OH

Rationale: We have chosen the multiple PI approach because developing innovative strategies to address the increasing burden of cardiovascular risk among people living with HIV (PLHIV) requires collaborative, interdisciplinary research. Furthermore, the two junior co-PI's ([name] and [name]) who are emerging as independent scientists in their field, will benefit from the experience of a senior implementation scientist ([name]) with a proven track record developing successful and scalable non-physician-led interventions to address cardiovascular risk factors in the VA and general US population.

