Screening: A research assistant will contact all subjects who do not opt out. Following a telephone script, the research assistant will describe the study in detail, ensure the patient is eligible and willing to participate, and schedule a baseline study visit at the next clinical visit with an HIV provider where they will be enrolled following the informed consent process described below. Study staff will make up to 3 attempts at telephone contact before marking a pre-screen eligible subject as “unable to contact.” In person contacts may be made at scheduled clinic visits. We will also seek to ensure that the contact information on file is correct by cross-referencing other sources in the electronic health systems at each site.

Finally, some patients may become aware of the study through their care team or word of mouth prior to receiving a pre-screening letter. These patients will be encouraged to contact study staff for screening (same script as above). In addition, a flyer will be posted at the Duke Infectious Diseases clinic as an additional avenue of recruitment. Additional across the board or site-specific strategies may be considered in the future if recruitment is a challenge.

We have previously estimated (2016 data; see table) that 900+ subjects in care at the 3 study sites would meet our inclusion criteria and would be eligible for enrollment. If we have trouble recruiting, we have access to additional community sites associated with our academic medical centers with similar demographics. Minority populations will be enrolled. While this group is considered a vulnerable population, the study team has considerable experience enrolling these participants and adapting interventions that are culturally sensitive. Given the increased prevalence of ASCVD risk factors in these populations, it is important that they are not excluded from participation in this study.

Table 4: Estimated eligible subjects at each clinic site based on 2016 data.				
	HIV viral load <200	Hypertension*	Hypercholesterolemia*	Both*
MetroHealth	1500 (85% of all HIV+)	491	501	286
Duke	1349 (71%)	605	397	291
University Hospitals	975 (89%)	550	485	334
* Defined here as a billing code/chart diagnosis OR on anti-hypertensive or cholesterol medication. The numbers for hypertension and hypercholesterolemia reflect ONLY HIV patients with HIV viral load <200 copies/ml.				

Aim 3 Enrollment:

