- 91 • Pregnant, breast-feeding, or planning a pregnancy during the study period
- 92 • Planning to move out of the area in the next 12 months
- 93 • Non-English Speaking

94 **Outcomes**

- 95 • **Primary:** 12-month change in systolic BP, calculated as the mean of two systolic BP readings
- 96 measured in the right arm, 1 minute apart.
- 97 • **Secondary:** 12-month change in non-HDL cholesterol, calculated as total cholesterol – HDL.
- 98 • **Tertiary:** change in the extended cascade categories for hypertension and hypercholesterolemia
- 99 ○ *Hypertension: 4-level category*
 - 100 ▪ Undiagnosed: hypertension is not listed on the EMR problem list
 - 101 ▪ Appropriately diagnosed: hypertension listed on the EMR problem list
 - 102 ▪ Appropriately managed: at least one medication prescribed for hypertension
 - 103 ▪ At treatment goal: <130 systolic
- 104 ○ *Hypercholesterolemia: 4-level category*
 - 105 ▪ Undiagnosed: hypercholesterolemia is not listed on the EMR problem list
 - 106 ▪ Appropriately diagnosed: hypercholesterolemia listed on the EMR problem list
 - 107 ▪ Appropriately managed: at least one medication prescribed for
 - 108 hypercholesterolemia
 - 109 ▪ At treatment goal, based on lifetime ASCVD risk
 - 110 - Low-moderate risk: <130 mg/dl
 - 111 - High: <100 mg/dl
 - 112 - Very high: <100 mg/dl
- 113 ○ Measured at each time point
 - 114 ▪ Diagnosis, management: EMR review by nurse
 - 115 ▪ At goal: measurement at that visit
- 116
- 117 • **Exploratory:** change in additional lipid measurements
 - 118 ○ Total cholesterol
 - 119 ○ Triglycerides
 - 120 ○ HDL
 - 121 ○ LDL
- 122

123 **Statistical Analysis**

124 ***Descriptive analyses***

125 Beginning with the chart review process, we will track ineligibility (number of patients, reasons),
126 declining to participate, and agreeing to participate but not proceeding to the initial visit. Once a patient
127 agrees to the phone screen, we will collect age, race, ethnicity, sex at birth, and gender. We will compare
128 demographics for those who enroll in the study to those who decline participation and to those who are
129 not eligible, using two sample t-tests (or nonparametric equivalent) and χ^2 tests. (*Table S1*)

130
131 We will further describe participating patients' characteristics (sociodemographic, lifestyle, medical
132 history). Continuous variables will be reported using mean (SD) or median (Q1, Q3) and categorical

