133 variables will be reported as N (%). These statistics will be reported for the overall sample and by study
 134 arm. (Table 1)

135

136 **Primary analyses**

137 The primary intervention effect analyses will utilize continuous, linear mixed models (LMM) to test for
 138 differences over time between the study arms. The general mean structure of the LMM we will use to
 139 examine the hypotheses is:

$$140 \quad Y_{ij} = \beta_0 + \beta_1 I(\text{month}=4) + \beta_2 I(\text{month}=8) + \beta_3 I(\text{month}=12) + \\
 141 \quad \beta_5 \text{arm} * I(\text{month}=4) + \beta_6 \text{arm} * I(\text{month}=8) + \beta_7 \text{arm} * I(\text{month}=12) + \beta_8 \text{clinic2} + \\
 142 \quad \beta_9 \text{clinic3}$$

143

144 where Y_{ij} represents the outcome of interest (i.e., SBP or non-HDL) for patient i at time j . In
 145 this model, we fit a common intercept and arm is the intervention group indicator. Similarly, time is
 146 classified, where for example, $I(\text{month}=12)$ is a dummy variable equal to 1 for the 12 month time point.
 147 Random intercepts will be included for each individual to account for correlation among repeated
 148 measurements over time. The primary analytic model will adjust for clinic site as fixed effects,
 149 represented with indicator variables clinic2 and clinic3, above. The mixed effects model parameters will
 150 be estimated and tested using SAS PROC MIXED (SAS Institute, Cary, NC), and the hypothesis of
 151 between-arm differences over time will be tested using estimate statements within PROC MIXED. In
 152 particular, β_7 , the estimated difference in outcome between arms at 12 months, will be the primary
 153 effectiveness outcome assessed.

154

155 For the tertiary outcome of cascade category, we will calculate an ordinal four-level variable at baseline,
 156 4, 8, and 12 months. We will use a proportional odds model fit via generalized estimating equations to
 157 examine differences over time between study arms. The proportional odds assumption will be assessed
 158 using score tests, and the model will be relaxed to partial proportional odds if necessary. Robust sandwich
 159 standard errors will be used to account for potential overdispersion and correlation among the repeated
 160 observations over time. Similarly to the primary analysis, the model will adjust for clinic site and include
 161 the same general mean model specification. The primary hypothesis will be tested via SAS PROC

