194 additional subgroup analysis stratified by treating physician (EXTRA-CVD investigator or not). The
195 primary analysis will be repeated with this stratification variable for our primary, secondary, and tertiary
196 outcomes. Intervention effects will be descriptively compared by treating physician status.

197 **Anticipated tables**

198 Table 1. Patient characteristics (demographic, medical history, lifestyle), overall and by treatment arm

199 Table 2. Primary, secondary, and tertiary outcomes at each time point, by treatment arm

200 Table 3. Intervention effects (LMM and proportional odds models) on primary, secondary, and tertiary
201 outcomes

202 Table 4. Moderation effects: clinic site; sex; baseline ASCVD risk

203 Table 5. Intervention effects stratified by treating physician (EXTRA-CVD investigator or not)

204 **Table 1. Patient characteristics at baseline, overall and by treatment arm**

Variable	Overall	Treatment arm	
		Intervention	Control
N			
Demographic characteristics			
Age (years), Mean (SD)			
Gender			
Male			
Female			
Transgender Male/Transman/FTM			
Unknown			
Ethnicity			
Hispanic/Latinx			
Non-Hispanic/Latinx			
Unknown			
Race			
African American/Black			
White			
Other race			
Multiracial			
Unknown			
Clinical characteristics			
Most recent CD4+ count			
Nadir CD4+ count			
Most recent viral load			
Antihypertensive medications			
None			
Thiazide diuretic			
ACE inhibitor			
Angiotension Receptor Blockers			
Beta Blockers			
Dihydropyridine CCB			
Non-dihydropyridine CCB			
Alpha-2-blocker			
Alpha-blocker			
Hydralazine			
Aldosterone antagonist			
Other			
Number of antihypertensive drugs, median (Q1, Q3)			
Cholesterol lowering drugs			
None			
Statin			
Ezetimibe			
Other			
ASCVD History			
Prior myocardial infarction			
Stroke/transient ischemic attack			
Other ischemic heart disease			
Peripheral artery disease			

Variable	Overall	Treatment arm	
		Intervention	Control
10-year ASCVD Risk score, 40+ years old and without prior history of events			
Low (<5)			
Borderline (5-7.4)			
Intermediate (7.5-19.9)			
High (≥ 20)			
Other medical history			
Diabetes			
Heart failure			
Current smoker			
Mental health disorder			

205

206

207 **Table 2. Primary, secondary, and tertiary outcomes at each time point, by treatment arm**

	Baseline		4 months		8 months		12 months	

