Intervention x Clinic 2						
Diagnosed						
Managed						
At treatment goal						
Intervention x Clinic 3						
Diagnosed						
Managed						
At treatment goal						
Sex						

Step 1: main effects						
Intervention						
Diagnosed						
Managed						
At treatment goal						
Sex: Female						
Diagnosed						
Managed						
At treatment goal						
Step 2: interaction						
Intervention						
Diagnosed						
Managed						
At treatment goal						
Sex: Female						
Diagnosed						
Managed						
At treatment goal						
Intervention x Female						
Diagnosed						
Managed						
At treatment goal						
Baseline ASCVD risk						
Step 1: main effects						
Intervention						
Diagnosed						
Managed						
At treatment goal						
ASCVD risk: High						
Diagnosed						
Managed						
At treatment goal						
Step 2: interaction						
Intervention						
Diagnosed						
Managed						
At treatment goal						

ASCVD risk: High						
Diagnosed						
Managed						
At treatment goal						
Intervention x High risk						
Diagnosed						
Managed						
At treatment goal						

215 Interaction terms are intervention*[moderator]*timepoint.

216 Reference groups: clinic 1 (clinic site), male (sex), low (ASCVD risk), and undiagnosed (extended cascade for HTN and DLD)

217 ASCVD status: High defined as $\geq 20\%$ 10-year risk or prior ASCVD; low defined as $< 20\%$ 10-year risk for ASCVD

218 **Table 5. Intervention effects stratified by treating physician (EXTRA-CVD investigator or not)**

	4 months	8 months	12 months
Continuous outcomes	β (95% CI)	β (95% CI)	β (95% CI)
Systolic blood pressure (mmHg) (primary)			
EXTRA-CVD investigator physician			
Non-EXTRA-CVD physician			
Non-HDL cholesterol (secondary)			
EXTRA-CVD investigator physician			
Non-EXTRA-CVD physician			
Ordinal outcomes	OR (95% CI)	OR (95% CI)	OR (95% CI)
Extended cascade category: systolic BP (tertiary)			
EXTRA-CVD investigator physician			
Undiagnosed	Ref.	Ref.	Ref.
Appropriately diagnosed			
Appropriately managed			
At treatment goal			
Non-EXTRA-CVD physician			
Undiagnosed	Ref.	Ref.	Ref.
Appropriately diagnosed			
Appropriately managed			
At treatment goal			
Extended cascade category: non-HDL (tertiary)			
EXTRA-CVD investigator physician			
Undiagnosed	Ref.	Ref.	Ref.
Appropriately diagnosed			
Appropriately managed			
At treatment goal			
Non-EXTRA-CVD physician			
Undiagnosed	Ref.	Ref.	Ref.
Appropriately diagnosed			
Appropriately managed			
At treatment goal			

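### SAP Table 5 asks for cascade odds ratios that the named proportional-odds model does not estimate, and the cascade GEE may leave the 12-month contrast unadjusted for baseline category

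*Combined protocol and SAP*

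**What the plan says.** The protocol (Statistical Considerations) and the SAP (Primary analyses) name a proportional-odds model fitted by GEE for the four-level cascade variable, relaxed to partial proportional odds if a score test requires it. On the mean structure the protocol says: "Similarly to the primary analysis, the model will adjust for clinic site and include the same general mean model specification". The SAP repeats this. The structure being copied has a common intercept, month indicators, arm-by-month terms and site. It has no arm main effect and no baseline covariate. On correlation the text says only: "Robust sandwich standard errors will be used to account for potential overdispersion and correlation among the repeated observations over time". The stated test is whether the estimated proportions per level differ between arms at 12 months.

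For participants treated by study investigators, the SAP (Subgroup analyses and moderation) says the "primary analysis will be repeated with this stratification variable for our primary, secondary, and tertiary" outcomes. The results go into SAP Table 5, "Intervention effects stratified by treating physician (EXTRA-CVD investigator or not"). Its ordinal block is headed as an odds ratio with 95% CI. Undiagnosed is marked as the reference at 4, 8 and 12 months, and the other three levels each have their own row. The footnote to the SAP moderation table also names undiagnosed as a reference group. SAP Table 3 gives one row per level under an N (%) label, with no effect measure.

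**The concern.** **Table 5.** A proportional-odds model has one cumulative odds ratio per visit. The partial version has one per cumulative split. Odds ratios of each level against a reference level belong to a multinomial logit, which the plan does not name. Two analysts could fill the shell with different quantities. The reference level may also be thin. It is defined as "Undiagnosed: hypertension is not listed on the EMR problem list", with a matching definition for cholesterol, whereas the protocol's feasibility counts (protocol Table 4) covered patients "Defined here as a billing code/chart diagnosis OR on anti-hypertensive or cholesterol medication".

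**Baseline.** In the linear mixed model the random intercept links month 0 to month 12, so a common intercept adjusts for baseline. A GEE does this only if the working association is modelled. Robust standard errors leave the estimate unchanged. The plan does not state the working association. If it is independence, the 12-month cascade contrast gives up precision that data already collected could supply, and it is exposed to chance baseline imbalance.

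**Working it through.** The plan states no power or effect figure for the cascade, so there is none to reproduce. The protocol's SBP and non-HDL sample sizes serve as a benchmark for the mechanism.

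**1. What the common intercept contributes.** Inputs (protocol, Power): SD 17 and r 0.4 for SBP; SD 41 and r 0.7 for non-HDL; 15% missing at 12 months; n = 300.

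- With the correlation modelled, 6 mmHg at 80% power needs 246 (protocol: 234) and 15 mg/dL needs 138 (protocol: 148). That is broadly the protocol's table.
- With the same mean model and correlation set to zero, N = 4(1.96+0.842)²·17²/6²/0.85 ≈ 297 for SBP. That is the 12-month-only figure. For non-HDL it is 276.
- Power at n = 300 (127.5 observed per arm): SE = 17·√(2/127.5) = 2.13, giving 80.5% against 87.1% with correlation modelled. For non-HDL it is 83.2% against 98.5%.

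So the common intercept helps only when correlation is modelled.

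**2. The same in the ordinal model.** Null simulations used n = 300, 350 trials per setting, latent r 0.4 and 0.7, and assumed level distributions 5/10/45/40% and 15/15/35/35%.

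- Under independence the planned 12-month coefficient correlates 0.999 with a fit to month 12 alone.
- Its slope on the baseline log-OR imbalance is 0.21–0.34 (r 0.4) and 0.59–0.68 (r 0.7). A chance baseline OR of 1.5 therefore carries through as 1.5^0.21 = 1.09 to 1.5^0.68 = 1.32.
- With baseline category as a covariate the slope is −0.11 to 0.10.

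**3. Power.** These runs used 3,000 trials per scenario, proportional odds under independence, and patient-clustered sandwich SEs. From the protocol: n, means, SDs, correlations, effects of 6 mmHg and 15 mg/dL, and 5/10/15% missing. Assumed:

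- split of undiagnosed/diagnosed/managed when not at goal: 10/15/75, 20/20/60 or 5/5/90
- chance of moving up one level per interval: 5% control, 10% intervention
- non-HDL goal <100 in 25% of participants; no non-HDL change in control
- effect linear to 12 months

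| Cascade | Lower-level status | Plan, independence | Baseline covariate | Gain (points) |
|---|---|---|---|---|
| Cholesterol | persistent | 59–60% | 75–79% | 15–19 |
| Cholesterol | half redrawn each visit | 60–61% | 69–71% | 9–11 |
| Cholesterol | fully redrawn | 60–61% | 68–71% | 8–11 |
| Hypertension | persistent | 51–52% | 60–69% | 8–18 |
| Hypertension | half or fully redrawn | 50–51% | 51–53% | 0–2 |

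Monte Carlo SE of each gain is at most 0.8 point. A second simulation (10/15/75 split, about 740–800 trials per setting) gave 61% vs 74%, 61% vs 69%, 51% vs 60% and 49% vs 50% for cholesterol persistent, cholesterol redrawn, hypertension persistent and hypertension redrawn.

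**4. Type I error.** It is 4.6–5.3% under either model when dropout is unrelated to outcome. Under mild assumed arm-specific dropout (per interval, not at goal/at goal: intervention 7/1%, control 5/5%) it is 6.4–6.8% under the plan against 5.0–5.1% for cholesterol, and 5.1–5.6% against 4.7–5.0% for hypertension.

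**5. Table 5, worked for hypertension with the 10/15/75 split.**

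- P(SBP<130) at 12 months: control Φ((130−144)/17) = 0.205; intervention Φ((130−138)/17) = 0.319.
- Lower-level split after three intervals: control 8.6/14.2/77.2%; intervention 7.3/13.4/79.3%.
- Cells (undiagnosed, diagnosed, managed, at goal): control 0.068, 0.113, 0.614, 0.205; intervention 0.050, 0.091, 0.540, 0.319.
- Cumulative ORs: diagnosed or better 19.14/13.67 = 1.40; managed or better 6.11/4.52 = 1.35; at goal 0.468/0.258 = 1.82.
- ORs against Undiagnosed: diagnosed 1.833/1.658 = 1.1; managed 10.88/9.01 = 1.2; at goal 6.43/3.01 = 2.1.

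Even a single cumulative OR of 1.5 with control levels 5/10/45/40% implies 1.05, 1.29 and 1.84 against Undiagnosed.

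**6. Size of the reference cell.** In the same case, 127.5 × 0.068 = 8.7 control and 127.5 × 0.050 = 6.3 intervention participants are Undiagnosed at 12 months. Over the three splits the range is 3–17 per arm (hypertension) and 2–13 (cholesterol). If investigators treat 20% of participants (assumed; 25.5 observed per arm), the chance that the cell is empty in at least one arm is 1 − (1−0.165)(1−0.273) ≈ 39% here. Over the splits it is 9–71% (hypertension) and 23–83% (cholesterol).

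**The case against.** Several points on the other side are fair.

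- The methods text names the model clearly, and Table 5 is a descriptive subgroup display on which no decision rests. Its three non-reference rows could be the three cumulative splits, mislabelled. The shell would still need correcting under that reading.
- The feasibility footnote describes 2016 counts. Eligibility itself requires neither a diagnosis nor a drug, since raised readings suffice. The footnote is therefore weak evidence of a thin reference level, and the empty-cell ranges rest on assumptions. The mismatch does not depend on them.
- The plan never says independence. Even under it, randomization protects the test, and the marginal contrast of proportions is a legitimate target. A baseline covariate is then an efficiency gain that changes the odds ratio to a conditional one. That stands, and is why standardized percentages belong with it.
- No power is claimed for the cascade. All splits and persistence patterns are assumed, and the hypertension gain may be nil. The simulated truth is also not exactly proportional (1.40, 1.35, 1.82), so the planned score test could lead to the partial model, which the simulation did not fit.
- The protocol promises results with and without multiple imputation, and the SAP plans attrition comparisons. Both count in its favour, but the only model named for imputed data is the mixed model: "Once missing values have been imputed, each multiply-imputed data set can be analyzed using the LMM".

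**Conclusion.** The Table 5 mismatch holds from the text alone: the named model and the shell describe different odds ratios.

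The baseline point is conditional on an independence working correlation, which the plan neither states nor excludes. Under that condition the 12-month cascade contrast is in effect a cross-sectional comparison. The cholesterol gain from adjustment, 8 to 19 power points, persists across every split and persistence pattern tried. The hypertension gain, 0 to 18 points, depends on how persistent lower-level status is, which the documents do not give.

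This is an improvement worth considering for a tertiary outcome. The primary SBP and secondary non-HDL analyses are not touched.

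**What to change.** 1. Redraw the SAP Table 5 cascade rows as one cumulative odds ratio per stratum and visit, or one per split under the partial model. Label the Table 3 cascade rows to match, and check the reference named in the moderation-table footnote.
2. Model the 4-, 8- and 12-month categories with baseline cascade category, site, visit and arm-by-visit, using robust SEs. State the working correlation; independence is enough once baseline is a covariate.
3. Report standardized percentages in each level by arm.
4. Keep participants with no baseline SBP or lipid value, by imputation or a baseline-missing level.
5. Apply the protocol's multiple imputation to the cascade as a sensitivity analysis, because a baseline covariate does not cover dropout driven by the 4- or 8-month category.

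The cost is SAP wording and table shells, with no new data. There are two downsides. The odds ratio becomes conditional (mean log OR 0.68 vs 0.53 for cholesterol and 0.56 vs 0.50 for hypertension; persistent, 10/15/75 split), hence item 3. Missing baselines also need handling. With an assumed 5–10% missing, dropping those participants gives power of 70–73% (cholesterol) and 59–61% (hypertension), a missing level gives 73–74% and 62–63%, and the plan as written under independence gives 60% and 50%.
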